Appendix D Interview Guide for VOC-triggered Telephone Calls

Instructions:

- *Establish* telephone contact with parent/caregiver when a potential VOC event is reported in the eDevice.
- *Check* the StudyWorks data reported from the eDevice either before or during the call.
- *Document* the call that is triggered by a potential VOC event in patient's medical records.
- *Note* the event details and whether or not event is considered to be fulfilling criteria for VOC endpoint or not.
- *Also note* any other AEs that come up during the conversation.
- *Also note* any change of medications that come up during the conversation.

When calling the parent/caregiver, the Investigator should introduce him/herself in an appropriate way and make sure he/she is speaking to the appropriate person.

In general, the parent/caregiver will be the appropriate person. The Investigator may decide to speak directly with a patient in late teenage age period, if judged more appropriate based on Investigator's thorough knowledge about the patient.

Cover the discussion items below during the normal doctor-parent/caregiver conversation in the phone call. Depending on the situation and the responses, additional questions may be needed for the Investigator to complete the required information in the eCRF.

Discussion item	Specific question (as applicable)

1. Collection of any VOC endpoints
 
Purpose: To ensure any VOC events not yet reported to Investigator are captured.
 
Questions should be tailored to ensure all the relevant data are collected for events meeting criteria for a VOC endpoint (painful crisis or ACS) so the eCRF can be completed*, examples:
 
 • Judge if event meets VOC definitions for this study • Start/stop • Treatment setting • Pain localisation • Type of analgesics taken (opioid/non-opioid) • Any other treatments given 
*Note that depending on where the event was treated, copies of medical records from other clinic or hospital may be needed.
	
“Has <<patient name>> experienced any painful episodes or had any episodes with chest problems, fever, and often also breathing symptoms, since the last time we talked?”


2. AE collection
 
Purpose: To collect any AEs other than the VOC event with onset since last contact and check status of ongoing AEs.
 
Use follow-up questions as needed to cover start/stop, outcome, any treatments provided, seriousness, severity, relationship to study drug or study procedures, and any changes to study drug treatment as outlined in the corresponding eCRF modules.
	
“Has<<patient name>> had any new health issues since the last time we talked?”
 
If this patient has any ongoing AEs recorded in the eCRF, ask about the status of those events:
 
“What about the <<ongoing event (e.g. cold, ankle sprain, etc.) we talked about last time? What happened with that?”

Discussion item	Specific question (as applicable)

Update information as needed on any ongoing AEs in the eCRF.
	

3. Concomitant medications
 
Purpose: To ensure concomitant medications are correctly captured.
 
Any changes to concomitant medications, both regularly taken and per needed, are to be further explored to ensure updated information is recorded in the eCRF.
 
Depending on what information on medications that came out from Discussion item 1 on the VOC event, any changes to medications may need to be further explored.
	
“Please can you tell me about all the medications that <<patient name>> has taken since the last time we talked?”
 
Then continue to prompt with
 
“Anything else?” until you have everything

4. eDevice functionality and usage
 
Purpose: To ensure eDevice is working OK and identify any need for re-training.
	
“Have you and <<patient name>> experienced any issues with using the eDevice?”
 
If any expected data in StudyWorks is missing:

Discussion item	Specific question (as applicable)

Any issues reported for the eDevice should be identified, further explored and resolved.
 
Remind parent/caregiver of the self-training availability in the eDevice.
 
Extra visits to site should be offered for hands-on re-training as needed.
	
“Is there anything more relating to << pain intensity / absence from school/work>> that you haven’t included?”
 
“Is there anything else you haven’t included?”
 
“Please can you tell me, if there is something we can do to help the eDevice recordings work better for you?”


5. Adherence to visit schedules and study procedures
 
Purpose: To reinforce adherence to study visits and procedures.
 
Provide reminder for the date and time for next visit to site or telephone visit.
 
Remind to not administer study drug at home in the morning of visits with PK/PD sampling.
 
Remind to bring all study drug bottles (including empty ones) to study visits.
	

Appendix E Guide for Scheduled Telephone Visits

Instructions:

- *Schedule* Telephone Visits monthly between On-site Visits.
- *Have the appropriate information* on the patient before the call. Check the StudyWorks entries made by the parent/caregiver/patient from their eDevice before the call.

Similar to On-site Visits, document the Telephone Visits in patient’s medical records. Notes are to include:

- Any adverse events,
- Whether the event fulfils criteria for VOC endpoint or not,
- Any changes of medications,
- And any use of contraceptives (applicable to females of childbearing potential and
- Consider if appropriate to discuss in telephone visits).

When calling the parent/caregiver, the Investigator should introduce him/herself in an appropriate way and make sure he/she is speaking to the appropriate person.

In general, the parent/caregiver will be the appropriate person. The Investigator may decide to speak directly with a patient in late teenage period, if judged more appropriate based on Investigator’s thorough knowledge about the patient.

Cover the discussion items below during the normal doctor-parent/caregiver conversation in the phone call. Depending on the situation and the responses, additional questions may be needed for the Investigator to complete the required information in the eCRF.

Discussion item	Specific question (as applicable)

6. AE collection
 
Purpose: To ensure AEs are captured during study.
	
“Has <<patient name>> had any new health issues since the last time we talked?”
 
If this patient has any ongoing AEs recorded in the eCRF, ask about the status of those events:

Discussion item	Specific question (as applicable)

Collect any AEs with onset since last contact, and check status of ongoing AEs.
 
As outlined in the corresponding eCRF modules, use follow-up questions as needed to cover:
 
 • Start/stop, • Outcome, • Any treatments provided, • Seriousness, • Severity, • Relationship to study drug or study procedures, • And any changes to study drug treatment 	
“What about the <<ongoing event (eg, cold, ankle sprain, etc.) >> we talked about last time? What happened with that?”


7. Collection of any VOC endpoints
 
Purpose: To ensure any VOC events not yet reported to Investigator are captured.
 
Questions should be tailored to ensure all the relevant data are collected for events meeting criteria for a VOC endpoint (painful crisis or ACS) so the eCRF can be completed*, examples:
 
 • Judge if event meets VOC definitions for this study • Start/stop • Treatment setting • Pain localisation • Type of analgesics taken (opioid/non-opioid) • Any other treatments given 	
Unless already sorted out during the AE Discussion Item above, ask specifically about VOC events:
 
“Has <<patient name>> experienced any painful episodes or had any episodes with chest problems, fever, and often also breathing symptoms, since the last time we talked?”

Discussion item	Specific question (as applicable)

*Note that depending on where the event was treated, copies of medical records from other clinic or hospital may be needed.
	

8. eDevice functionality and usage
 
Purpose: To ensure that the eDevice is working OK and identify any need for re-training.
 
Questions should be tailored based on entries made in StudyWorks, eg, if perfect compliance to weekly assessments of school/work absence but no VOC events, question could focus on ensuring no potential VOC events have been missed.
 
Potential problems with using the eDevice should be further explored and resolved.
 
Remind parent/caregiver of the self-training availability in the eDevice.
 
Offer extra visits to site for hands-on re-training as needed.
	
“Have you and <<patient name>> experienced any issues with using the eDevice?”
 
If any expected data in StudyWorks is missing:
 
“I can see that you have not recorded much about <<pain intensity / absence from school/work>> in your eDevice.”
 
“Is there anything more relating to << pain intensity / absence from school/work>> that you haven’t included?”
 
“Is there anything else you haven’t included?”
 
“Please can you tell me if there is something we can do to help the eDevice recordings work better for you?”

Discussion item	Specific question (as applicable)

9. Some VOC event details need to be recorded in the eDevice
 
Purpose: To ensure the VOC details to be reported by the parent/caregiver/patient for any VOC events are captured in the eDevice.
 
Provide reminder to record any painful crises and ACS events, and to do a daily VOC pain rating while the event is ongoing, regardless of where such events are treated.
 
Also provide reminder to bring the eDevice with them in case they seek medical care.
	

10. Parents/caregivers to contact the study site in case a suspected VOC
 
Purpose: To ensure a timely collection of event-related information to have high-quality VOC endpoint data.
 
Provide reminder to call site within 72 hours in the event of any painful crises and/or ACS.
 
Also check that parent/caregiver knows contact details to the site.
	

Discussion item	Specific question (as applicable)

11. Concomitant medications
 
Purpose: To ensure concomitant medications are captured during study.
 
Any change to concomitant medications is to be further explored to ensure updated information is recorded in the eCRF.
	
“Please can you tell me about all the medications that <<patient name>> has taken since the last time we talked?”
 
Then continue to prompt with
 
“Anything else?”
 
until you have everything.

12. Use of contraceptive methods (when applicable)
 
Purpose: To reduce risk for pregnancies during study in fertile female participants.
 
Remind parent/caregiver/patients that female, fertile participants should not get pregnant during study. An individually appropriate contraceptive method should be discussed (See study protocol section 3.8) and the importance of use re-enforced.
 
Consider if appropriate to discuss contraceptives in Telephone Visits or only at On-site Visits.
	
“You know that young girls should not get pregnant while in this study. Is there a need for <<patient name>> to use any contraceptive method to not get pregnant? What is she using?”

13. Adherence to visit schedules and study procedures
 
Purpose: To reinforce adherence to study visits and procedures.
 
Remind patient about the date and time for next visit to site or telephone visit.
	

Discussion item	Specific question (as applicable)

Remind to not administer study drug at home in the morning of visits with PK/PD sampling.
 
Remind to bring all study drug bottles (including empty ones) to study visits.
	

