3.9 Permanent discontinuation or temporary stop of investigational product

3.9.1 Permanent discontinuation

Patients may be permanently discontinued from IP in the following situations:

1. The patient (or caregiver) is at any time free to discontinue treatment or advise the patient to discontinue treatment, without prejudice to further treatment
2. AE, as judged by Investigator, that with continued treatment would put the patient at undue risk
3. Severe non-compliance with the study protocol, as judged by Investigator and/or AstraZeneca
4. Severe illness or risk to the patient as judged by the Investigator
5. Any major bleeding, for bleeding definitions see Section [6.3.8](#).
6. Repeated minor bleedings not needing medical intervention unless clearly not related to study drug (eg, minor trauma during playing), as judged by the Investigator
7. For females of childbearing potential, who are sexually active and where effective contraception cannot be secured, the study treatment must be discontinued
8. In the event of pregnancy, study drug should be immediately permanently discontinued. The patient is encouraged to continue to be followed in the study according to the study plan.
9. Conditional or Abnormal TCD findings, ie, TAMMV values are ≥ 153 cm/sec using TCDi technique (corresponding to ≥ 170 cm/sec by the non-imaging technique), indicating an increased risk of stroke.
10. Pathological findings on any imaging technique indicating increased risk of ischaemic or haemorrhagic stroke
11. TIA or stroke (ischaemic or haemorrhagic)
12. Need for chronic transfusion therapy
13. Findings indicating impaired liver function and/or coagulopathy:

- ALT or aspartate aminotransferase (AST) $>5 \times \text{ULN}$, ALT or AST $>3 \times \text{ULN}$ and total bilirubin level $>2 \times \text{ULN}$ (unless bilirubin increase clearly explained by haemolysis), INR >1.5 . For potential Hy's Law laboratory criteria: the elevation in transaminases must precede or coincide with (ie, on the same day as) the elevation in total bilirubin, but there is no specified timeframe within which the elevations in transaminases and total bilirubin must occur.

14. Renal failure requiring dialysis
15. Patients with clinical symptoms of bradyarrhythmia as judged by the Investigator and/or ECG findings of significant sinus pauses or high degree atrioventricular block
16. Development of proliferative retinopathy.

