6.1 Definition of adverse events

An AE is the development of any untoward medical occurrence in a patient or clinical study patient administered a medicinal product and which does not necessarily have a causal relationship with this treatment. An AE can therefore be any unfavourable and unintended sign (eg, an abnormal laboratory finding), symptom (eg, nausea, chest pain), or disease temporally associated with the use of a medicinal product, whether or not considered related to the medicinal product.

The term AE is used to include both serious and non-serious AEs and can include a deterioration of a pre-existing medical occurrence. An AE may occur at any time, including run-in or washout periods, even if no study treatment has been administered.

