6.3.5 Adverse events based on signs and symptoms

All AEs spontaneously reported by the patient or care provider or reported in response to the open question from the study site staff: ‘*Have you/the child had any health problems since the previous visit/you were last asked?*’, or revealed by observation will be collected and recorded in the eCRF. When collecting AEs, the recording of diagnoses is preferred (when possible) to recording a list of signs and symptoms. However, if a diagnosis is known and there are other signs or symptoms that are not generally part of the diagnosis, the diagnosis and each sign or symptom will be recorded separately.

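### The telephone scripts' adverse-event question is narrower than the protocol's own AE question and definition, and neither script prompts for bleeding

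*Protocol*

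**What the plan says.** Protocol Section 6.1 defines an AE broadly: it "can include a deterioration of a pre-existing medical occurrence". Section 6.3.5 gives the open question that staff are to ask: "Have you/the child had any health problems since the previous visit/you were last asked".

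The two telephone guides use other words. Appendix D item 2 (calls triggered by a possible VOC) and Appendix E item 6 (scheduled monthly calls) both script whether the patient has "had any new health issues since the last time we talked". Each guide then adds a second AE probe: "If this patient has any ongoing AEs recorded in the eCRF, ask about the status of those events".

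The calls cover more than this. Both guides ask whether the patient has "experienced any painful episodes or had any episodes with chest problems, fever, and often also breathing symptoms, since the last time we talked", and both ask for all medications taken since the last contact. The instruction beside the AE question in Appendix E is "Collect any AEs with onset since last contact, and check status of ongoing AEs", and both guides say that "additional questions may be needed for the Investigator to complete the required information in the eCRF".

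Bleeding events enter the data as AEs (Protocol Section 6.3.8; SAP Section 3.4.4). Minor bleeding there includes any overt bleeding below the two higher categories. Neither guide mentions bleeding.

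**The concern.** An open AE question finds what it invites families to report. The word *new* invites them to leave out a known problem that has become worse, which Section 6.1 says is an AE. A child with occasional nosebleeds before randomisation who now has them more often is the natural example.

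Bleeding is the safety issue on which the protocol puts most weight: Section 1.3 says tolerance for it will be low and that the DMC will watch it closely. Minor bleeds are often untreated and soon over, so their count depends heavily on what families are asked. They are tabulated by arm (Protocol Section 8.5.4), and one of the discontinuation criteria in Section 3.9.1 refers to "Repeated minor bleedings not needing medical intervention". The guides give named prompts to pain, chest symptoms and, in Appendix E, contraception, so a targeted prompt was clearly considered workable in a call.

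**Working it through.** No stated figure in the plan rests on this point, so there is none to reproduce. The check has three parts.

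**1. What each scripted prompt reaches.** AEs are collected only from randomisation (Section 6.3.1), so a condition present at baseline is not on the list of ongoing AEs unless it has since been recorded as one.

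| Event since last contact | Scripted prompt in the call that reaches it |
|---|---|
| New condition, or a first bleed | The question on new health issues |
| Worsening of an AE already in the eCRF | The status probe |
| Pain, chest, fever or breathing symptoms | The VOC prompt |
| Worsening that was treated with a medicine | The medication prompt, indirectly |
| Other untreated worsening of a baseline condition not recorded as an AE | None |
| Untreated minor bleed of a kind the child has had before | None, if the family does not regard it as new |

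The gap is the last two rows.

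**2. Share of contacts made by telephone.** Inputs are the visits with AE collection in Protocol Tables 2 and 3. The End of Study visit replaces the site visit due in the final month, and the safety follow-up visit is counted. With T telephone contacts and S site contacts after randomisation, the share is T/(T + S), or T/(T + S + 1) if the randomisation visit (Visit 2) is also counted.

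| Follow-up | T | S | Without Visit 2 | With Visit 2 |
|---|---|---|---|---|
| 12 months (planned minimum) | 7 | 7 | 7/14 = 50.0% | 7/15 = 46.7% |
| 18 months (planned mean) | 11 | 9 | 11/20 = 55.0% | 11/21 = 52.4% |
| 24 months (maximum) | 15 | 11 | 15/26 = 57.7% | 15/27 = 55.6% |

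These are scheduled contacts only. As an upper bound, suppose that every VOC triggers an extra Appendix D call at the rates assumed in Protocol Section 8.2 (2.0 per year on placebo, half that on ticagrelor). At 18 months, counting Visit 2, the share becomes (11 + 3)/(21 + 3) = 58.3% on placebo and (11 + 1.5)/(21 + 1.5) = 55.6% on ticagrelor. Calls that replace site visits under Section 3.9.4 would raise the share. The early end of study in SAP Section 3.1.4.1 could shorten follow-up and lower it.

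**3. What a loss would do.** Let a fraction c of minor bleeds be captured, the same in both arms, with true event rates λT (ticagrelor) and λP (placebo). The observed rates are cλT and cλP. Their ratio is still λT/λP, while their difference is c(λT − λP), smaller than the true one. For patients with at least one bleed the loss is less than 1 − c, because a patient with several bleeds still counts if one is missed. Neither document gives a bleeding rate, or a value of c for either wording, so no size can be computed.

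**The case against.** The strongest reply is that the script is not the collection rule. The guides call for AEs with onset since last contact, treat the scripted questions as applicable to the situation, place them within an ordinary conversation and allow more questions. Sections 6.1 and 6.3.5 are not limited to site visits, so they govern calls too. All of this stands, and it rules out reading the calls as asking about new issues and nothing else. It does not remove the mismatch: the words supplied to about 80 centres in some 18 countries are narrower than the rule, and the further questions are left to discretion.

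A reader might also infer that whatever a call misses is never asked for again. The documents do not establish that. The 6.3.5 question refers to the previous visit as well as to when the family was last asked. That phrase is ambiguous, because calls are numbered visits too. Every site visit also has an examination and a medication review, and new or aggravated findings are AEs (Section 6.3.6). The back-up is partial: most site visits use the brief examination (Section 5.2.2: general appearance, respiratory, cardiovascular, abdomen), and a nosebleed that has stopped leaves nothing to find.

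The missing bleeding prompt might be read as a contradiction of the protocol. It is not. The 6.3.5 question does not name bleeding either, a first nosebleed is a new health issue, and open rather than solicited questioning is a legitimate choice. The DMC's bleeding triggers in Section 1.5.2 concern fatal bleeding, spontaneous intracranial haemorrhage and bleeding that needs medical intervention; these depend much less on how a call is worded.

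**Conclusion.** The mismatch of wording is real and can be read directly from the text. The scripted question in both guides is narrower than Sections 6.1 and 6.3.5, and it leaves one identifiable group of AEs without a prompt in calls. The absence of a bleeding prompt is a missed opportunity on the main safety risk, not an inconsistency.

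Calls make up about half of scheduled AE contacts. It is tempting to say more than half; that holds at 18 and 24 months on the counts above but not at 12 months, where the share is 47–50%.

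It is also tempting to conclude that events are under-collected and that ticagrelor will look safer. The documents show only that some worsening conditions and untreated minor bleeds may be missed. The study is double-blind with one script for both arms, so any loss should be largely non-differential: absolute differences in event rates would shrink and ratios would be little affected. That rests on similar capture in the two arms, which is plausible but untested. This is a moderate data-collection point.

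**What to change.** In Appendix D item 2 and Appendix E item 6, replace the scripted AE question with the Section 6.3.5 wording and add *or has anything got worse*. This brings the calls into line with the protocol's own definition and needs no new procedure.

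As a cheap addition, use one standard bleeding prompt (for example nosebleeds, gum bleeding, bruising, heavy periods) in identical words for all patients, at every call and every site visit. Using it at calls alone would make elicitation differ by type of contact.

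The cost is script wording, a few seconds per contact and somewhat more minor events recorded in both arms. If the wording changes during the study, the date should be recorded, since counts before and after may not be comparable. Data from calls already made cannot be repaired by rewording; for those, the clinical study report should state the limitation beside the minor-bleeding counts.
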